## LIST OF ABBREVIATIONS

AE	adverse event
ALT	alanine aminotransferase
ALP	alkaline phosphatase
AST	aspartate transaminase
ATC	anatomical therapeutic chemical
BLQ	below the limit of quantitation
BMI	body mass index
BPM	beats per minute
CHB	chronic hepatitis B
CI	confidence interval
ECG	electrocardiogram
eCRF	electronic case report form
eGFR	estimated glomerular filtration rate
FAS	full analysis set
FU	follow-up
GLPS	Global Product Safety
HBcrAg	hepatitis B core-related antigen
HBV	hepatitis B virus
HBeAb	hepatitis B e antibody
HBeAg	hepatitis B e antigen
HBsAb	hepatitis B surface antibody
HBsAg	hepatitis B surface antigen
HLGT	high level group term
HLT	high level term
ID	Identification
IMP	Investigational Medicinal Product
LLT	lower level term
LLOQ	lower limit of quantitation
LOQ	limit of quantitation
MedDRA	Medical Dictionary for Regulatory Activities
NUC	nucleos(t)ide
INR	international normalized ratio
Peg-IFN	pegylated interferon
PK	pharmacokinetics
PT	preferred term
Q1	first quartile
Q3	third quartile
RBC	red blood cell

RNA	ribonucleic acid
SAE	serious adverse event
SAP	statistical analysis plan
SD	standard deviation
SE	standard error
SOC	system organ class
TAF	tenofovir alafenamide
TE	treatment-emergent
TFFU	treatment-free follow-up
TFLs	tables, figures, and listings
TND	target not detected
ULN	upper limit of the normal range
WBC	white blood cell
WHO	World Health Organization

## 1. INTRODUCTION

This statistical analysis plan (SAP) describes the statistical analysis methods and data presentations to be used in tables, figures, and listings (TFLs) in the clinical study report (CSR) for Study GS-US-464-4437. This SAP is based on the study protocol amendment 3 dated 11 March 2019 and the electronic case report form (eCRF). The SAP will be finalized before the final analysis. Any changes made after the finalization of the SAP will be documented in the CSR.

### 1.1. Study Objectives

The primary objectives of this study are as follows:

- To evaluate the safety and tolerability of the 12 week treatment regimens of GS-9992 plus tenofovir alafenamide (TAF) or commercially available nucleos(t)ides (NUCs)

- **Groups 1-3 and 5**

To evaluate the antiviral activity of 12 weeks of GS-9992 plus TAF versus TAF alone in viremic chronic hepatitis B (CHB) subjects as measured by the proportion of subjects with  $\geq 0.5 \log_{10}$  IU/mL decline from baseline at Week 12 in circulating serum quantitative hepatitis B surface antigen (qHBsAg)

- **Group 4**

To evaluate the antiviral activity of 12 weeks of GS-9992 with commercially available NUC(s) in virally suppressed CHB subjects as measured by the proportion of subjects with  $\geq 0.5 \log_{10}$  IU/mL decline from baseline at Week 12 in circulating serum qHBsAg

The secondary objectives of this study are as follows:

- **Groups 1-3 and 5**

To evaluate the safety and tolerability of the 48 week treatment regimens as assessed by review of the accumulated safety data

To evaluate the antiviral activity of 12 weeks of GS-9992 plus TAF versus TAF alone in CHB subjects as measured by the proportion of subjects with  $\geq 1 \log_{10}$  IU/mL decline from baseline at Week 12 in circulating qHBsAg

To evaluate the proportion of hepatitis B e antigen (HBeAg) positive CHB subjects who achieve HBeAg loss and seroconversion during 12 weeks of GS-9992 plus TAF versus TAF alone and after GS-9992 discontinuation through 48 weeks

To evaluate the proportion of CHB subjects who achieve hepatitis B surface antigen (HBsAg) loss during 12 weeks of GS-9992 plus TAF versus TAF alone and after GS-9992 discontinuation through 48 weeks

To evaluate the incidence of drug resistance mutations during 48 weeks of treatment

To characterize steady-state pharmacokinetics (PK) of study drugs

To evaluate the change from baseline in hepatitis B virus (HBV) deoxyribonucleic acid (DNA) and qHBsAg in CHB subjects during 12 weeks of GS-9992 plus TAF versus TAF alone and after GS-9992 discontinuation through 48 weeks

- **Group 4**

To evaluate the proportion of subjects experiencing HBV virologic breakthrough (2 consecutive visits of HBV DNA  $\geq$  69 IU/mL) during 12 weeks of GS-9992 treatment

To evaluate the antiviral activity of 12 weeks of GS-9992 in CHB subjects as measured by the proportion of subjects with  $\geq$  1 log10 IU/mL decline from baseline at Week 12 in circulating qHBsAg

To evaluate the proportion of HBeAg-positive CHB subjects who achieve HBeAg loss and seroconversion during 12 weeks of GS-9992 and after GS-9992 discontinuation through 48 weeks

To evaluate the proportion of CHB subjects who achieve HBsAg loss during 12 weeks of GS-9992 and after GS-9992 discontinuation through 48 weeks

To characterize steady-state PK of study drugs

To evaluate the change from baseline in qHBsAg in CHB subjects during 12 weeks of GS-9992 and after GS-9992 discontinuation through 48 weeks

CCI [REDACTED]

[REDACTED]

[REDACTED]

[REDACTED]

[REDACTED]

## 1.2. Study Design

This is a Phase 2, randomized, open-label, active-controlled study to evaluate the safety and antiviral activity of GS-9992 plus TAF or commercially available NUC in CHB subjects.

Approximately 120 chronic, immune-active, HBV-infected adults without cirrhosis will be enrolled; including 100 viremic subjects not currently on HBV NUC and 20 virally suppressed subjects on a commercially available NUC.

**Groups 1 and 2:** Approximately 40 viremic subjects will be randomized in a 3:1 ratio to the following:

- Group 1: Approximately 30 subjects will be administered GS-9992 50 mg (2 × 25 mg capsules) once daily one hour before or one hour after a meal plus TAF 25 mg once daily with food for 12 weeks then TAF 25 mg once daily with food for 36 weeks
- Group 2: Approximately 10 subjects will be administered TAF 25 mg once daily with food for 48 weeks

Randomization will be stratified by HBeAg status (positive or negative) at screening with approximately 40% of HBeAg negative subjects enrolled.

**Group 3:** Approximately 30 viremic subjects will be administered GS-9992 200 mg (2 x 100mg) once daily one hour before or one hour after a meal plus TAF 25 mg once daily with food for 12 weeks then TAF 25 mg once daily with food for 36 weeks.

Approximately 40% of subjects enrolled in Group 3 will be HBeAg negative.

[figure not shown]
**Group 4:** Approximately 20 virally suppressed subjects currently being treated with a commercially available NUC(s) for CHB will be administered GS-9992 100 mg tablet once daily one hour before or one hour after a meal for 12 weeks.

Approximately 50% of subjects enrolled in Group 4 will be HBeAg negative. Subjects will remain on their current commercially available NUC(s) therapy for the duration of the study. All subjects will be followed through Week 48.

**Group 5 (Hong Kong):** Approximately 30 viremic subjects may be enrolled and assigned:

GS-9992 400 mg (2 x 200 mg tablets) once daily one hour before or one hour after a meal plus TAF 25 mg once daily with food for 12 weeks then TAF 25 mg once daily with food for 36 weeks.

**Figure 1. Study Schema**

*\*Group 4: Subjects who discontinue NUCs should be followed in Treatment-Free Follow-up*

### **24 Week Treatment-Free Follow-up (TFFU)**

Subjects that meet any one of the following criteria will be followed for 24 weeks or until the initiation of alternative CHB therapy, whichever comes first:

- Subjects that discontinue all HBV therapy (eg, GS-9992 and/or TAF or commercially available NUC), for any reason;
- Subjects with HBsAg loss confirmed at least 12 weeks apart should discontinue all HBV therapy following confirmation.

The total time to complete all study visits is up to approximately 79 weeks including the following periods:

- Up to 45 day (6 to 7 weeks) screening period
- A 48-week study period

Groups 1, 3 and 5: 12 week treatment of GS-9992 plus TAF followed by TAF only treatment

Group 2: 48 weeks of TAF only treatment

Group 4: 12 week treatment of GS-9992 plus commercially available NUC followed by NUC only

- Up to 24-week TFFU period

The schedule of assessments is provided as an appendix to the SAP ([Appendix 1](#)).

### **1.3. Sample Size and Power**

Due to the exploratory nature of this study, the sample size was not determined by any formal power calculation. The number of subjects in each treatment group was decided based on clinical experience.

## **2. TYPE OF PLANNED ANALYSIS**

### **2.1. Interim Analysis**

After all subjects in Group 3 have completed the study, all the data including Groups 1-4 through TFFU and Group 5 through Week 12 have been cleaned and finalized, the interim analysis of the data will be performed into three parts as follows:

#### **2.1.1. Analysis for 12 Week Regimen**

The Analysis for 12 Week Regimen will include data collected through 30 days after the last dose of GS-9992 (Groups 1, 3-5) or 30 days after 12 weeks treatment of TAF (Group 2).

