**Table 7-1. GS-9992 Dose Modification and Monitoring**

Liver Toxicity	Action
Confirmed ALT $\geq 10 \times$ ULN without evidence of hepatic toxicity as defined below	Discuss with the Medical Monitor if GS-9992 should be dose reduced by 50% or discontinued if the safety of the subject is of immediate concern. Subject should be monitored weekly or more frequently if clinically indicated until ALT $< 5 \times$ ULN
Confirmed ALT $> 2 \times$ nadir, with evidence of hepatic toxicity, defined as any one of the following: 
 
• Total bilirubin <math>> 2 \times</math> baseline or nadir AND <math>> \text{ULN}</math> in the absence of Gilbert's disease
 
• Elevated INR <math>> 0.5</math> above baseline AND <math>> \text{ULN}</math>
 
• Abnormal serum albumin <math>> 1 \text{ g/dL}</math> decrease from baseline
 
	Permanently discontinue GS-9992. Subject should be monitored weekly until ALT $< 5 \times$ ULN, and total bilirubin and INR values return to normal or baseline levels
Confirmed ALT $> 2 \times$ Baseline and $\geq 5 \times$ ULN without evidence of hepatic toxicity, as defined above	Continue GS-9992, ALT should be evaluated every 2 weeks or more frequently as clinically needed, until ALT $< 5 \times$ ULN

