#### **3.8.2. Analysis Visit Windows**

Subject visits might not occur on protocol-specified days. Therefore, for the purpose of analysis, observations will be assigned to analysis windows.

- For Groups 1-3 and 5

Data collected up to 3 days after the last dose date of GS-9992 or TAF, whichever comes last, will be considered as on-treatment data whereas data collected afterwards will be considered as posttreatment data.

- For Group 4

Data collected up to 3 days after the last dose date of GS-9992 or 3 days after the subjects have discontinued commercially available NUC(s), whichever comes last, will be considered as on-treatment data whereas data collected afterwards will be considered as posttreatment data.

On-treatment data will be mapped to the analysis windows defined in [Table 3-1](#), [Table 3-2](#), [Table 3-3](#) and [Table 3-4](#).

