## 7.1.5. Treatment-Emergent Adverse Events

### 7.1.5.1. Definition of Treatment-Emergent Adverse Events

For the **Analysis for 12 Week Regimen**, treatment-emergent adverse events (TEAEs) are defined as follows:

- For subjects treated with GS-9992 and TAF or commercially available NUC(s) (ie, Group 1, 3, 4 and 5):

Any AEs with an onset date on or after the first dose date of any study drug and no later than 30 days after permanent discontinuation of GS-9992

Any AEs leading to premature discontinuation of any study drug during the first 12 weeks (ie, from Day 1 to Day 84).

- For subjects treated with TAF only (ie, Group 2):

For those who remained on TAF treatment for the first 12 weeks plus 30 days (ie, from Day 1 to Day 114):

- Any AEs with an onset date on or after the first dose of TAF and no later than 30 days after the first 12 weeks treatment of TAF (ie, no later than Day 114)

For those who prematurely discontinued TAF during the first 12 weeks plus 30 days (ie, from Day 1 to Day 114):

- Any AEs with an onset date on or after the first dose of TAF and no later than 3 days after permanent discontinuation of TAF or up to Day 114, whichever comes earlier
- Any AEs leading to premature discontinuation of TAF

For the **Analysis for 48 Week Regimen**, TEAEs are defined as follows:

- For subjects treated with GS-9992 and TAF (ie, Group 1, 3 and 5):

Any AEs with an onset date on or after the first dose date of any study drug and no later than 3 days after permanent discontinuation of TAF or 30 days after permanent discontinuation of GS-9992, whichever comes last

Any AEs leading to premature discontinuation of any study drug during the 48 weeks treatment

- For subjects treated with TAF only (ie, Group 2):

Any AEs with an onset date on or after the first dose date of TAF and no later than 3 days after permanent discontinuation of TAF

Any AEs leading to premature discontinuation of TAF during the 48 weeks treatment

- Subjects treated with GS-9992 and commercially available NUC(s) (ie, Group 4) are not included in treatment-emergent **Analysis for 48 Week Regimen**.

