#### For the **Analysis for 12 Week Regimen**:

- For subjects treated with GS-9992 and TAF or commercially available NUC(s) (ie, Group 1, 3 -5):

30 days after permanent discontinuation of GS-9992

- For subjects treated with TAF only (ie, Group 2):

For those who remained on TAF treatment for the first 12 weeks plus 30 days (ie, from Day 1 to Day 114):

- 30 days after the first 12 weeks treatment of TAF (ie, no later than Day 114)

For those who prematurely discontinued TAF during the first 12 weeks plus 30 days (ie, from Day 1 to Day 114):

- 3 days after permanent discontinuation of TAF or up to Day 114, whichever comes earlier

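### SAP 2.1.1 closes the 12-week data 30 days after the last GS-9992 dose with no Week 12 floor; read literally, this can discard Week 12 HBsAg values taken on TAF and conflicts with SAP 3.8.2

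*SAP*

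**What the plan says.** **Data cut.** For the GS-9992 groups, SAP 2.1.1 reads "The Analysis for 12 Week Regimen will include data collected through 30 days after the last dose of GS-9992 (Groups 1, 3-5"; for the control it reads "30 days after 12 weeks treatment of TAF (Group 2". SAP 2.2 gives the final analysis the same three parts, so this is not only an interim rule.

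**Adverse events.** SAP 7.1.5.1 counts events in the GS-9992 groups "no later than 30 days after permanent discontinuation of GS-9992". It adds an exception: "Any AEs leading to premature discontinuation of any study drug during the first 12 weeks (ie, from Day 1 to Day 84". A Group 2 subject still on TAF is counted "no later than 30 days after the first 12 weeks treatment of TAF (ie, no later than Day 114".

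**Laboratory abnormalities.** For the 12-week analysis, SAP 7.2.3.1 closes the GS-9992 groups at "30 days after permanent discontinuation of GS-9992" and Group 2 subjects still on TAF at Day 114.

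**Visit windows.** For Groups 1-3 and 5, SAP 3.8.2 says "Data collected up to 3 days after the last dose date of GS-9992 or TAF, whichever comes last, will be considered as on-treatment data". Table 3-1 maps on-treatment qHBsAg on Days 72 to 99 to Week 12, nominal Day 85.

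**Protocol.** The synopsis (Criteria for Evaluation) runs the primary antiviral analysis to Week 12 without reference to the last GS-9992 dose. It runs primary safety to four weeks after that dose, as does 8.6. Section 8.3 counts a missing primary endpoint as a failure.

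**The concern.** The protocol foresees GS-9992 stopping by itself. Table 7-1 has its own action, "Permanently discontinue GS-9992", TAF is handled separately in Table 7-2, and 6.6 asks sites to keep subjects who stop dosing in the study. A Week 12 sample taken on TAF is therefore expected from such a subject.

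Under 2.1.1 that sample can fall after the data cut; under 3.8.2 it is valid on-treatment Week 12 data. Two programmers could each follow the SAP and report different primary response rates. A Group 2 subject still on TAF cannot lose a Week 12 value this way, so any error falls on one side of the comparison.

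The same moving cut gives these subjects a shorter period in the 12-week adverse event and laboratory tables than Group 2, and safety of the 12-week regimens is a primary objective.

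**Working it through.** **The plan's own figure.** Group 2 cut: 12 × 7 = 84, and 84 + 30 = Day 114. This matches SAP 7.1.5.1. A subject who completes GS-9992 on Day 84 is also cut at Day 114, so the rules agree for completers.

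**When a Week 12 value is lost under a literal 2.1.1.** With the last GS-9992 dose on Day s, the cut is s + 30. A sample on Day d is excluded if s + 30 < d, that is, s ≤ d − 31.

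- First day of the window, d = 72: s ≤ 41, and the whole window is lost.
- Nominal visit, d = 85: s ≤ 54. For the ±3-day visit window, d = 82 gives s ≤ 51 and d = 88 gives s ≤ 57.
- Last day of the window, d = 99: s ≤ 68, so the whole window is kept from s = 69.
- Group 2: Day 114 lies past Day 99, so nothing is lost while TAF continues.

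**Days missing from the 12-week safety period.** 114 − (s + 30) = 84 − s.

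| Last GS-9992 dose | Cut | Days short of 114 | Day 85 sample |
|---|---|---|---|
| Day 14 | Day 44 | 70 | excluded |
| Day 28 | Day 58 | 56 | excluded |
| Day 56 | Day 86 | 28 | kept |
| Day 84 | Day 114 | 0 | kept |

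A stop on Day 28 leaves 58 of 114 days, or 51%.

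**How many subjects.** Protocol 1.2.2 describes the earlier trial.

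- At 50 mg, 2 of 16 stopped for an adverse event. One withdrew from the study at Week 2; with no Week 12 sample, such a subject is a failure under either rule. The other stopped for ALT above 10 × ULN, apparently the Week 4 stop described in the same section. This leaves 1 of 16.
- At 100 mg (17 active) no adverse event led to discontinuation. Among the first 200 mg subjects (12 active) none stopped.
- Pooled over these three cohorts: 1/(16 + 17 + 12) = 1/45 = 2.2%.
- Per group of 30: 30/45 = 0.7 to 30/16 = 1.9 subjects.

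**Effect on the response rate.** Only responders change it, at 1/30 = 3.3 points each. The documents give no planned response rate, so I assume 5% to 31%. The upper figure is the share of 25 mg subjects (5 of 16) with a maximal HBsAg fall above 0.5 log10. With 1 or 2 early stoppers:

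- lowest expected loss: 0.05 × 1/30 = 0.2 points
- highest expected loss: 0.31 × 2/30 = 2.1 points
- ceiling if both are responders: 2/30 = 6.7 points

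**Against the precision of the comparison.** As an illustration, take strata of 18 and 12 against 6 and 4 (40% HBeAg-negative), with 5 and 4 responders against none. The Mantel-Haenszel difference, with squared weights in the variance, is 0.300 (95% CI 0.062 to 0.538). Losing one HBeAg-positive responder gives 0.267 (0.033 to 0.500).

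**The case against.** The strongest reply is that 2.1.1 only describes scope and sets no endpoint rule. The endpoint definition, the full analysis set, 3.8.2, Table 3-1 and the protocol's Week 12 horizon all ignore the GS-9992 stop date. Read together, they keep the Week 12 value. This stands in part: the loss is an unresolved conflict, not a certainty. But 2.1.1 says which data enter the analysis, and nothing in the SAP subordinates it to 3.8.2.

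On safety, the stop-based window follows protocol 8.6, which speaks of four weeks where the SAP uses 30 days. That stands, and the window should not be replaced.

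Four stronger readings are tempting, and the documents do not support them:

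- **That subjects who stop for a flare are responders, so the bias is shown.** The 25 mg subject with a Week 4 flare and a 1.01 log10 HBsAg fall was dose-reduced, not stopped. The protocol reports no HBsAg result for anyone who stopped.
- **That 6 to 13 points of a group's response are at stake.** This applies 1 or 2 of 16 to 30 subjects, counts the subject who withdrew, uses only the 50 mg cohort and treats every stopper as a responder. It is a ceiling.
- **That delayed hepatic events are hidden.** In Groups 1, 3 and 5 they remain in the 48-week tables, and SAP 7.2.4 plans the liver and ALT-flare summaries on that set. Adverse events leading to discontinuation in Days 1 to 84 stay in the 12-week tables.
- **That only GS-9992 subjects are ever cut short.** Group 2 subjects who stop TAF early are cut 3 days after stopping for adverse events and laboratory abnormalities.

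**Conclusion.** The point holds as an ambiguity in which data feed the primary endpoint, together with a 12-week safety period that is shorter for some GS-9992 subjects than for Group 2. It concerns subjects in Groups 1, 3 and 5 who stop GS-9992 early and continue TAF. The primary endpoint is affected only if 2.1.1 overrides 3.8.2 and, for the nominal visit, the last GS-9992 dose is on or before Day 54.

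The likely size is about one or two subjects per group of 30 and an expected 0.2 to 2.1 points. This rests on stopping rates from an earlier monotherapy trial and on assumed response rates. The 400 mg dose in Group 5 has no 12-week stopping data in the protocol. With no hypothesis test and an illustrative interval about 48 points wide, the severity is moderate to minor, not must-fix.

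Group 4 has the same moving cut and is left out of the 48-week treatment-emergent analysis, so its later events reach only the listings; it has no TAF control to be compared with.

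**What to change.** 1. Add to SAP 2.1.1 that the Week 12 efficacy analyses use every on-treatment record in the Table 3-1 window, as defined in 3.8.2, whatever the date of the last GS-9992 dose.
2. Keep the SAP's summary to 30 days after the last GS-9992 dose as the 12-week safety analysis under protocol 8.6. Beside it, in 7.1.5.1 and 7.2.3.1, add an adverse event and laboratory summary to a common Day 114 for Groups 1-3 and 5 while TAF continues. Flag events more than 30 days after GS-9992 stopped.

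Day 114 lies beyond the end of the Week 12 window and restores the 84 − s missing safety days; nothing changes for subjects who complete GS-9992. The cost is one sentence of SAP text and one extra set of safety tables. No new data are needed.

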#### **2.1.2. Analysis for 48 Week Regimen**

The Analysis for 48 Week Regimen will include data collected to the end of the completion of 48 Week study period.

#### **2.1.3. TFFU Analysis**

The TFFU analysis will be conducted for subjects who entered the 24-week TFFU period.

### **2.2. Final Analysis**

After all subjects have completed the study, outstanding data queries have been resolved or adjudicated as unresolvable, and the data have been cleaned and finalized, the final analysis of the data will be performed. The final analysis consists of three parts: analysis for 12 Week regimen, analysis for 48 Week regimen, and TFFU analysis.

### **3. GENERAL CONSIDERATIONS FOR DATA ANALYSES**

Analysis results will be presented using descriptive statistics. For categorical variables, the number and percentage of subjects in each category will be presented; for continuous variables, the number of subjects (n), mean, standard deviation (SD) or standard error (SE), median, first quartile (Q1), third quartile (Q3), minimum, and maximum will be presented.

By-subject listings will be presented for all subjects in the All Randomized/Enrolled Analysis Set and sorted by subject ID, visit date, and time (if applicable). Data collected on log forms, such as adverse events (AEs), will be presented in chronological order within the subject. The treatment group to which subjects were randomized (Group 1 and 2) or enrolled (Group 3-5) will be used in the listings. Age, sex at birth, race, and ethnicity will be included in the listings, if space permits.

#### **3.1. Analysis Sets**

Analysis sets define the subjects to be included in an analysis. Analysis sets and their definitions are provided in this section. The analysis set will be identified and included as a subtitle of each table, figure and listing.

For each analysis set, the number and percentage of subjects eligible for inclusion, as well as the number and percentage of subjects who were excluded and the reasons for their exclusion, will be summarized by treatment group.

A listing of reasons for exclusion from analysis sets will be provided by subject.

